11.8. Disease Follow-up

All participants who discontinue from study treatment for reasons other than radiologically confirmed disease progression or withdrawal of consent will be followed to obtain information about disease status. Participants who discontinue study treatment due to radiologically confirmed disease progression will not need to complete Disease Follow-up. The first disease follow-up will begin 12 weeks (±4 weeks) after the last dose of study drug and an MRI will be required at this visit.

All subsequent disease follow-up will be conducted by telephone every 16 weeks (\pm 4 weeks) thereafter and a review of the participant's medical records for disease status changes will be performed. Disease follow-up will continue for up to 2 years after last dose of study treatment or until radiological progression, start of new subsequent therapy/surgery, or withdrawal of consent. Any SAE occurring during this follow-up period must be reported if assessed as related to study drug by the Investigator.

Information to be collected will include:

- Date of contact
- Status of disease (ie, radiological disease progression, yes/no)
- Date of progression
- Subsequent TGCT therapy and/or surgery (refer to Section 11.9.11)

11.9. Study Procedures

All study procedures will be conducted as shown in Table 1, Table 2, and Table 3.

11.9.1. Demographic/Medical History/Baseline Signs and Symptoms

Data collected will include general participant demographic information (participant's year of birth, age, gender, and race), relevant medical history, and details of prior TGCT therapy, if applicable.

The medical history shall include a complete review of systems, past medical and surgical histories, and any allergies. Medical history includes any significant conditions or diseases that stopped at or prior to informed consent. Ongoing conditions are considered concurrent medical conditions; if possible, the start date and grade for these comorbidities must be documented. Baseline signs and symptoms related to TGCT should also be documented (ie, joint pain, swelling).

11.9.2. Confirmation of Tenosynovial Giant Cell Tumor Diagnosis

A histopathological report confirming TGCT diagnosis must be available prior to randomization. If a prior histopathology report is not available in the medical record, a biopsy of the tumor must be performed to confirm TGCT diagnosis and eligibility as described in Section 11.3.

Participants who require a biopsy to confirm TGCT diagnosis should sign a pre-screen consent form before the biopsy. TGCT diagnosis must be confirmed by a local pathologist prior to randomization. The screening MRI must be performed at least 30 days **after** the biopsy to allow for adequate healing of the biopsy site and accurate tumor measurement.

11.9.3. Assessment of Pain and Stiffness Symptoms

To meet eligibility, participants must have symptomatic disease with at least moderate pain or at least moderate stiffness. Both of these symptoms should be assessed using scales provided by the Sponsor. Moderate pain or stiffness is defined as at least a 4 out of 10, with 10 describing the worst condition. During screening, both assessments should be documented in the medical records.

11.9.4. Surgical Assessments

The surgical assessment questionnaire will be provided by the Sponsor and completed by a qualified person (eg, orthopedic surgeon) to document a participant's surgical status at screening (ie, surgical risk, complexity of surgery, probability of complete resection). The surgical assessment questionnaire may be completed based on an orthopedic consultation/clinic visit that was performed within 6 months prior to screening, provided the participant received no treatment for TGCT in the interim. After screening, surgical assessment questionnaire should also be completed prior to surgery for participants who proceed to surgery during the study, to capture post-treatment status.

11.9.5. Physical Examination

A full physical examination should be performed at screening and at End of Part 1 visit.

At all other study visits, including EOT visit, physical examinations will be abbreviated and driven by clinical findings and/or participants complaints.

11.9.6. Vital Signs, Weight, and Height

Vital sign measurements will be collected after the participant has been at rest for at least 5 minutes. Vital signs will include sitting blood pressure, heart rate, respiratory rate, and temperature. On days when PK sampling is performed, vital sign measurements should be obtained after ECG and prior to the PK sampling timepoint.

Weight will be collected at all study visits.

Height will only be obtained at screening.

11.9.7. Pregnancy Test

Pregnancy test will be performed at the site in all female participants of childbearing potential. A negative serum β -hCG test is required at screening. A negative serum or urine test will be performed within 3 days of the first dose at Cycle 1 Day 1 and Cycle 1 Day 1 crossover. At subsequent clinic visits, pregnancy tests will be performed by serum or urine testing through Week 49. After Week 49, serum or urine tests will be performed monthly. In between clinic visits, pregnancy testing may be performed at home. If pregnancy testing is performed at home, then the Investigator should contact the participant to confirm pregnancy result. Refer to the relevant schedule of assessments for timing of pregnancy testing. If urine pregnancy test result is positive, the study drug must be held and a confirmation serum pregnancy must be performed. If pregnancy is confirmed by serum test, refer to Section 11.9.14.4.2 for information on pregnancy reporting and study withdrawal.

11.9.8. Hepatitis B/C Test

Serology testing for hepatitis B and C at screening will be performed by a central laboratory. Hepatitis B results will include hepatitis B surface antigen (HbsAg), hepatitis B core antibody (anti-HBc), and hepatitis B surface antibody (anti-HBs). Guidance on interpretation of hepatitis B test results will be per Centers for Disease Control and Prevention (CDC) guidelines (CDC, 2020). Hepatitis C results will include hepatitis C virus antibody (anti-HCV).

11.9.9. Prior and Concomitant Medications and Procedures

Prior medications including prescription and nonprescription medications, vitamins, and supplements, and nondrug therapies or procedures taken or performed within 30 days before first dose of study drug will be recorded as prior medications.

Concomitant mediations include any medication as described above (except study drug) taken from first dose of study drug through Safety Follow-up (ie, 30 days after last dose). The type, dose, and route of administration must be documented in the medical records.

11.9.10. Narcotic Analgesic Use

The use of narcotic analgesics will be collected in a patient diary beginning at screening for 1 year (through Cycle 12/Cycle 6 Crossover) or until EOT, whichever comes first. The medication, date, time, number of tablets/patches and total dose for each administration will be recorded.

Examples of narcotic analgesics are:

- Acetaminophen with codeine
- Codeine
- Fentanyl
- Hydrocodone-acetaminophen
- Hydromorphone
- Morphine sulfate
- Oxycodone
- Oxycodone with acetaminophen
- Tramadol

11.9.11. TGCT Treatment and/or Surgery After Treatment Discontinuation

Any new TGCT therapies (systemic or radiation) and/or surgery since discontinuation of study treatment must be recorded. The new TGCT therapy and/or surgery must be noted including details such as the date of surgery, reason for surgery and outcome of surgery or start date of new TGCT therapy.

11.9.12. Collection of Photographic Images of the Affected Joint

A photographic image of the affected joint will be collected, if site agrees and is allowed per IRB/Independent Ethics Committee (IEC)/ Research Ethics Board (REB) and patient consents, at screening and if visual improvement or worsening of swelling is evident during study participation. Images will be taken at the same location at screening and throughout the study. If taken, the images will be shared with the Sponsor. The data will be used as a supplement for disease assessment and may be included in publication for scientific conferences or in the literature. Participants with identifiable marks (eg, birth marks and tattoos) close to the affected joint will not take part.

11.9.13. Efficacy Assessments

Efficacy assessments will be conducted as shown in Table 1, Table 2, and Table 3.

For participants on placebo continuing to Part 2, the efficacy assessment performed for the End of Part 1 visit will serve as both the last assessment of Part 1 and as the baseline assessment used for Part 2.

11.9.13.1. Imaging for Response Assessments

TGCT participants will have an MRI of their affected joint according to the Schedules of Assessments. Tumor response will be assessed by the Investigator using RECIST v1.1 and assessed by an independent radiological reviewer(s) designated by the Sponsor using RECIST v1.1 (see Appendix 3). Modified RECIST (mRECIST; see Appendix 4), TVS (see Appendix 5), and TDS (see Appendix 6) will be generated by the central imaging vendor. Central review is performed for all MRI imaging performed for 2 years after first dose of study drug, after which the images will be read by the site. During the 2 years that IRR is required,

images will not be read in real time by the IRR vendor and tumor responses will not be shared with the Investigators unless a suspected local radiological disease progression is reported by the Investigator for expedited IRR.

A separate Imaging Manual will be provided by the central imaging vendor. The Manual will provide instructions for site training, secure transfer of images to the central vendor, parameters for images acquisition and MRI image Quality Control (QC) process.

During screening, the baseline MRI image will be sent to the central vendor to qualify the participant. All baseline images are required to pass acceptance criteria including eligibility criteria in order for the participant to be randomized. The vendor will provide documentation that the image has passed acceptance criteria and met eligibility criteria. If the image is found not acceptable per the parameters in the manual, a repeat MRI will be required.

For 2 years after first dose of study drug, a similar QC process will be followed for all MRI images. If the image is found not acceptable per the parameters in the manual, a repeat MRI will be requested.

If an Investigator suspects disease progression during the period of 2 years after first dose of study drug, an MRI should be immediately submitted to the central imaging vendor with a request for an expedited read for potential disease progression to determine eligibility to crossover to Part 2 or to discontinue study drug as described in Section 10.5.

11.9.13.2. Range of Motion Assessment

The ROM of the affected and contralateral non-affected joint will be assessed using goniometry according to the relevant schedule of assessments. The modality of assessment will be active, ie, measuring a motion produced by the participant's voluntary, unassisted muscle contraction, and passive, ie, measuring a motion produced by the application of external force by an examiner. Active and passive assessments of the affected joint will be performed at screening and thereafter according to the relevant schedule of assessments. Active and passive assessments of the non-affected contralateral joint will only be performed at screening and End of Part 1 visit.

The joint, side of body, motions assessed, and degrees measured (the start and end position of motion) will be recorded for active and passive motion. Results should be documented on the ROM form provided by the Sponsor. Adequately trained site personnel (physiotherapist or orthopedic surgeon) who are blinded to study treatment should perform the ROM assessment. Every effort should be made to have the same assessor conduct all ROM assessments for each participant throughout the protocol. All motions applicable to a specific joint should be collected for the duration of the clinical study.

11.9.14. Safety Assessments

Safety assessments will be conducted as shown in Table 1, Table 2, and Table 3.

11.9.14.1. Electrocardiogram

Electrocardiograms will be performed according to the relevant schedule of assessments.

For each ECG timepoint, single 12-lead ECGs will be obtained using a local ECG machine. ECG intervals (QT, RR, QTcF, HR, and QRS) will be collected. Unscheduled, single 12-lead ECGs may be obtained by the site at any time during the study if clinically indicated.

11.9.14.2. Clinical Laboratory Tests for Safety

Clinical laboratory tests are summarized in Table 14 and will be performed by a central laboratory, except for urinalysis, according to the relevant schedule of assessments. Additional (unscheduled) local laboratory samples for safety or repeat tests may be collected, if clinically indicated.

All laboratory test results that are abnormal and considered clinically significant must be reported as AEs (Section 11.9.14.3.1). If a clinically significant laboratory AE is supported by a corresponding local lab result, but not by the central lab result, the local lab result will be recorded. All samples will be collected in accordance with acceptable laboratory procedures and graded for toxicity as defined by the National Cancer Institute (NCI)-CTCAE, v5.0.

Available local laboratory test results should be used for treatment management decisions and initial assignment of CTCAE grading. Every effort should be made to discuss any changes to study drug dosing with the Sponsor before implementation, and only if not feasible beforehand, to inform the Sponsor within the same day. Central laboratory results will be used for final assignment of CTCAE grading. In the case of different grades associated with local versus central laboratory results for AEs, the Investigator should determine which laboratory values will be used to document grading of AEs. The local vs central laboratory result with the highest grade should be considered to document grading of AEs.

Hematology	Coagulation	Chemistry	Urinalysis (dipstick) ^a
Hematocrit	Activated partial	Alanine	Hemoglobin
Hemoglobin	thromboplastin time	aminotransferase	Glucose
Platelet count	Prothrombin time	Albumin	Ketone
Red blood cell count	International	Alkaline phosphatase	Protein
White blood cell count with differential	normalized ratio	Aspartate aminotransferase	Specific gravity
		Bicarbonate	
		Calcium	
		Cholesterol	
		Chloride	
		Creatine phosphokinase	
		Creatinine	
		Gamma-glutamyl transferase	
		Glucose	
		Potassium	
		Sodium	
		Magnesium	
		Phosphorus	
		Total bilirubin	
		Conjugated (direct) bilirubin	
		Unconjugated (indirect) bilirubin ^b	
		Total protein	
		Triglycerides	
		Blood urea nitrogen	

Table 14: Clinical Laboratory Tests

^a An additional microscopic examination will be performed if any dipstick analytes are 2+ or higher. A participant should undergo further assessment (eg, a 24-hour urine collection) if the protein analyte is \geq 2+.

^b Will be calculated by central laboratory.

11.9.14.3. Adverse Events and Serious Adverse Events

11.9.14.3.1. Adverse Event

An AE is any untoward medical occurrence in a clinical study participant. The occurrence may or may not have a causal relationship with the investigational treatment. This includes any newly occurring event or previous condition that has increased in severity or frequency after the ICF is signed. Illnesses present prior to the participant signing the ICF are considered to be pre-existing conditions and are documented on the medical history eCRF. Pre-existing conditions that worsen during the study are entered on the AE eCRF.

Pregnancy is not considered an AE, although a participant will be withdrawn from the study if a pregnancy occurs. The pregnancy, including a partner's pregnancy, must be reported to Deciphera or designee, and additional follow-up may be required as described in Section 11.9.14.4.2.

11.9.14.3.2. Serious Adverse Event

An SAE is any AE, occurring at any dose and regardless of causality, that:

- Results in death (ie, the adverse event causes or leads to death)
- Is life threatening. The participant is at immediate risk of death from the reaction as it occurs. This does not include reaction that, had it occurred in a more severe form, might have caused death
- Requires inpatient hospitalization or prolongation of existing hospitalization
- Results in persistent or significant disability/incapacity (eg, a substantial disruption of a person's ability to conduct normal life functions)
- Results in a congenital anomaly/birth defect
- An important medical event that may not result in death, be immediately life threatening, or require hospitalization may be considered to be an SAE when, based upon appropriate medical judgment, the event may jeopardize the participant and may require intervention to prevent one of the other outcomes listed above

Admission to a hospital or an inpatient unit for a nonmedical reason (ie, social stay admission) during the study in the absence of untoward medical occurrence will not be considered as an SAE but will be captured as an AE.

Hospitalization due to worsening of pre-existing conditions should be reported as an SAE.

Clarification must be made between the terms "serious" and "severe", because they are not synonymous. The term "severe" is often used to describe the intensity (severity) of a specific event, as in mild, moderate, or severe myocardial infarction. The event itself, however, may be of relatively minor medical significance, such as a severe headache. This is not the same as "serious," which is based on participant/event outcome or action criteria described above and is usually associated with events that pose a threat to a participant's life or functioning. Seriousness, not severity, serves as a guide for defining regulatory reporting obligations.

11.9.14.3.3. Relationship to Study Drug

The assessment of the study drug relationship to each AE will be documented based on the temporal relationship and the best clinical judgment of the Investigator. Causality will be determined using the 2 categories below. All study drugs are considered when defining causality.

• **Related:** The AE is known to occur with the study drug or there is a reasonable possibility that the study drug caused the AE, and there is a temporal relationship

between the study drug and event that supports relatedness. Reasonable possibility means that there is evidence to suggest a causal relationship between the study drug and the AE.

• Not Related: There is no reasonable possibility that the treatment with study drug caused the event, the temporal relationship between the study drug and event onset does not support relatedness, or an alternate etiology has been established.

11.9.14.3.4. Severity Assessment

The Investigator must determine and record the severity of all serious and nonserious AEs. The NCI-CTCAE, v5.0, must be used for grading the severity of AEs (NCI-CTCAE, 2020). When there is a change in severity of an existing adverse event including improvement or worsening of an event, a new AE should be reported.

The severity of an AE that does not appear in the CTCAE scale must be determined according to Table 15.

Classification	Definition
Grade 1 (Mild)	Asymptomatic or mild symptoms; clinical or diagnostic observations only; intervention not indicated.
Grade 2 (Moderate)	Minimal, local, or noninvasive intervention indicated; limiting age-appropriate instrumental Activities of Daily Living.
Grade 3 (Severe)	Severe or medically significant but not immediately life-threatening; hospitalization or prolongation of hospitalization indicated; disabling; limiting self-care Activities of Daily Living.
Grade 4 (Life threatening)	Life-threatening consequences; urgent intervention indicated.
Grade 5 (Death)	Death related to AE.

Table 15:Severity Grading Scale

Abbreviation: AE=adverse event

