11.9.14.3.9. Monitoring and Recording Adverse Events

The AE (including SAEs) reporting period will begin after a participant signs the main ICF and will continue until completion of the Safety Follow-up Visit or 30 days after the final dose of study drug. Any SAE having an onset after the Safety Follow-up Visit will not be collected or reported unless the Investigator feels that the event may be related to the study drug. Only SAEs that are assessed by the Investigator as related to the biopsy will be collected after a participant signs the pre-screening consent and until the participant has signed the main ICF.

Participants will be instructed by the Investigator or designee to report the occurrence of any AE. All volunteered, elicited, and observed AEs are to be recorded.

If a participant begins a new TGCT therapy, the safety reporting period ends at the time the new treatment is started; however, death must always be reported when it occurs during the safety reporting period irrespective of intervening treatment.

The Investigator will assess all AEs regarding any causal relationship to the study drug, the intensity (severity) of the event, action taken, and participant outcome (see Section 11.9.14.3).

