12.4.6. Safety Analyses

Participants from the Safety Set will be included in safety analyses.

AEs will be coded using the MedDRA for purposes of summarization. All AEs occurring on study will be listed in by participant data listings. Treatment-emergent AEs will be tabulated, where treatment emergent is defined as any AE that occurs after administration of the first dose of study drug and through 30 days after the last dose of study drug. Tabulations for all TEAEs, treatment-emergent SAEs, related TEAEs, dose reduction, dose interruptions, and discontinuation of study drug due to AE will be produced. By participant listings will be provided for deaths, SAEs, and AEs leading to discontinuation of study drug.

Change from baseline in clinical laboratory parameters will be summarized across time on study, and the frequency of clinically significant abnormal laboratory values will be tabulated.

Changes in ECG intervals (QT, RR, QTcF, HR, QRS) and vital sign parameters (including systolic and diastolic blood pressure, heart rate, respiration rate, and temperature) will be summarized over time in a similar fashion to laboratory parameters, and any abnormal values will be tabulated. Changes in ECG findings will be presented in data listing format.

Additional safety assessments such as ECGs will be listed by participant.

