9.11. Safety Analysis

All safety analyses will be conducted on the SAF. If there are both local and central assessments in the same nominal visit, then the central assessment will be used for analyses. The safety data will be summarized following two different approaches. The first approach will be limited to data from Part 1 and will focus on comparisons between participants who received vimseltinib versus participants who received placebo during this period. The second approach will combine data from both Part 1 and Part 2 (including extension period) and will focus on the observations and assessments while participants are receiving vimseltinib. Therefore, in this second approach, participants randomized to Placebo in Part 1 who crossed over to vimseltinib in Part 2, will have as their reference day the first dose date of vimseltinib in Part 2, and their data from Part 1 while receiving placebo will be excluded.

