9.11.2. Adverse Event

Adverse events (AEs) will be coded using MedDRA version 26.0 (or higher). The intensity of AE will be documented using the National Cancer Institute (NCI) Common Terminology Criteria for Adverse Event (CTCAE) version 5.0.

A treatment-emergent AE (TEAE) is defined as any AE that occurs or worsens after administration of the first dose of study drug and through 30 days after the last dose of study drug or the day before the start of new antitumor therapy. Drug-related AEs reported after 30 days following the last dose of study drug will also be considered as treatment-emergent.

Drug related AEs include AEs reported as 'POSSIBLY RELATED' and 'RELATED'.

Summary statistics (frequency and percentages of participants) will be presented by SOC and PT by treatment group for following:

- Overall summary of TEAEs
- Any TEAE
- Any nonserious TEAE
- Any Grade 3/4 TEAE
- Any serious TEAE

- Any drug-related TEAE
- Any Grade 3/4 drug-related TEAE
- Any drug-related serious TEAE
- Any TEAE leading to dose modification (including dose reduction and interruption)
- Any drug-related TEAE leading to dose modification (including dose reduction and interruption)
- Any TEAE leading to treatment discontinuation
- Any drug-related TEAEs leading to treatment discontinuation
- Any TEAE leading to death

The following will be tabulated by SOC, PT, and maximum severity grade:

- TEAEs
- Serious TEAEs
- Drug-related TEAEs
- Drug-related serious TEAEs

The following will be presented by PT:

- TEAEs
- TEAEs of Grade 3/4
- Serious TEAEs
- Drug-related TEAEs
- Drug-related TEAEs of Grade 3/4
- Drug-related serious TEAEs

If a SOC or PT was reported more than once for a participant, the participant would only be counted once in the incidence for that SOC or PT. For participants experiencing the same PT at multiple severity levels, the occurrence of the AEs with the maximum severity will be counted in the analysis of incidence by severity. For participants experiencing the same PT at multiple relationship levels, the occurrence of the AEs with the strongest relationship to study drug will be counted in the analysis of incidence by relationship to study drug.

The following listings will be provided for the SAF:

- All AEs (including AEs occurring prior and after the TEAE period)
- Serious Adverse Events
- Death
- AEs leading to study drug discontinuation
- AEs leading to dose modification (reduction or interruption)

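### An adverse event record opened only because an event improved can be flagged as treatment-emergent, because the SAP neither links severity-change records nor compares grades

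*Protocol*

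**What the plan says.** - **Recording.** Protocol 11.9.14.3.4 (Severity Assessment): "When there is a change in severity of an existing adverse event including improvement or worsening of an event, a new AE should be reported".
- **Collection window.** Protocol 11.9.14.3.9: "The AE (including SAEs) reporting period will begin after a participant signs the main ICF". Screening may last 42 days, so events can start before any dose.
- **TEAE definition.** Protocol 12.4.6: "treatment emergent is defined as any AE that occurs after administration of the first dose of study drug". SAP 9.11.2 adds worsening: "defined as any AE that occurs or worsens after administration of the first dose of study drug". SAP Section 1 makes the SAP the governing text where the two differ.
- **Pooled vimseltinib summary.** SAP 9.11 combines Part 1 and Part 2. Placebo participants who cross over "will have as their reference day the first dose date of vimseltinib in Part 2". The same section then removes what was recorded for them before crossover: "their data from Part 1 while receiving placebo will be excluded".
- **De-duplication.** SAP 9.11.2: "If a SOC or PT was reported more than once for a participant, the participant would only be counted once in the incidence". Neither document has any other rule that joins records.

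**The concern.** The recording rule works on records and the TEAE definition works on dates. Together they let an improvement look like a new event. Suppose an event of Grade 2 begins in screening or on placebo and falls to Grade 1 after the reference dose. The site opens a second record with a later start date. A program that compares start date with dose date flags it, although nothing new has happened and the participant is getting better.

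The pooled summary matters most. It is meant to describe safety on vimseltinib, and through crossover participants it can take in events that began on placebo. Splitting one event into several records also breaks up its duration, which SAP 8.4.2 indicates will be calculated.

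**Working it through.** The plan states no figure on this point to reproduce. The check is to apply the rules as written, then see what limits the size.

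**Step 1. Follow one record through the rules.**
1. An event starts after main consent and before the reference dose. It is an AE but not a TEAE.
2. After the reference dose it drops a grade. Protocol 11.9.14.3.4 calls for a new AE, dated at the change.
3. That record starts after the dose. On its dates it meets the *occurs* limb of SAP 9.11.2, and no grade condition removes it.
4. The once-per-term rule acts only among TEAEs. The original record lies outside that set: by date in Part 1, and by exclusion of placebo-period data in the pooled summary. There is nothing for the new record to be merged with.

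**Step 2. Compare a literal rule with a linked rule on example records.** The literal rule flags a record if its start day is 1 or later, counted from the reference dose. The linked rule also requires its grade to exceed the pre-dose grade, taken as 0 if there is no earlier record.

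| Example | Records (day, grade) | Literal | Linked |
|---|---|---|---|
| Screening event improves | Day -5, G2; Day 10, G1 | 1 | 0 |
| Placebo-period event improves after crossover | Day -30, G3; Day 8, G2 | 1 | 0 |
| Pre-dose event worsens | Day -5, G1; Day 10, G2 | 1 | 1 |
| New event | Day 10, G1 | 1 | 1 |

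Only the improvement records change status. Each example has at most one pre-dose record, so the highest and the last pre-dose grade are the same.

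**Step 3. Where it acts.**
- Part 1: the reference is the first dose of either study drug, so screening events that ease after it are flagged in both arms.
- Pooled summary: for crossovers the reference moves to the first vimseltinib dose, so placebo-period events that ease afterwards are flagged under vimseltinib.
- Not affected: conditions present before consent. Protocol 11.9.14.3.1 treats these as medical history, entered as AEs only if they worsen.

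**Step 4. Size.** Neither document gives the rate of ongoing events at crossover or the chance that they ease by a grade. The ceiling on crossovers is the planned placebo arm, 40. It is not expected to be reached, because crossover is optional and the sample size allows for 15% dropout. For illustration only, with all 40 crossing over:

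affected participants = 40 × q × r, where q is the assumed proportion with an AE ongoing at crossover and r the assumed proportion of these whose event eases by a grade without resolving.

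- q = 10%, r = 25%: 40 × 0.10 × 0.25 = 1, and 1/120 = 0.8%.
- q = 30%, r = 50%: 40 × 0.30 × 0.50 = 6, and 6/120 = 5.0%.
- q = 50%, r = 75%: 40 × 0.50 × 0.75 = 15, and 15/120 = 12.5%.

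The width of this range shows that the documents do not determine the size. These are also counts of participants with at least one such record, not increases in a reported rate. The any-TEAE rate moves only for a participant with no other TEAE, and a preferred-term rate only for one with no other TEAE of that term. The Grade 3/4 tables gain an entry only when a Grade 4 event eases to Grade 3.

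**The case against.** The best defence is that the definition is meant at event level. If every severity-change record were a fresh occurrence, the word *worsens* in the SAP would be redundant, because a worsening also opens a new record. The AE definition in Protocol 11.9.14.3.1 covers new events and conditions that become more severe or more frequent, and leaves out improvement. Protocol Table 17 treats improvement as an outcome of an existing AE. On this reading an improvement record is not a TEAE.

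This stands as evidence of intent. A reader might infer that the plan deliberately counts improvements as vimseltinib TEAEs, and the documents do not support that. But no rule carries the intent out, and the instruction to open a new AE on improvement conflicts with it. A link in the case report form or a programming specification could resolve this, but neither document describes one.

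Three further points stand and limit the concern:
- Any overcount is toward more reported harm, in line with the conservative date imputation in SAP 8.4.2. All AEs, including those before the TEAE period, are listed, so an original event can be traced.
- Drug-related tables depend on the investigator's causality judgement, which weighs timing. An event known to predate vimseltinib is unlikely to be called related.
- The pooled summary carries no hypothesis test.

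**Conclusion.** The concern holds as an unresolved conflict between the recording rule and the TEAE definition. Under a date-based flag, the lower-grade continuation of a pre-dose event counts as a TEAE in both arms in Part 1. In the pooled summary, the continuation of a placebo-period event counts as a vimseltinib TEAE. This rests on the literal text and on there being no linking rule elsewhere.

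Two stronger conclusions may tempt a reader. One is that the randomised safety comparison is biased against vimseltinib. The documents do not show this: the same rule applies to both arms, and screening events precede randomised treatment. The other is that TEAE rates are inflated by a stated number of percentage points. The documents give no basis for such a number, and participants with an affected record are not the same as a rise in a table rate. What can be said is that at most 40 crossover participants are exposed in the pooled summary, that the effect on any single preferred term is likely smaller, and that it is toward over-reporting. This is a minor point, worth settling because settling it is cheap.

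**What to change.** Add to SAP 9.11.2:

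1. Link records of the same continuous event and take onset from the first record.
2. Flag the linked event as treatment-emergent only if its onset is on or after the relevant first dose, or its grade after that dose exceeds the last grade before it. For crossover participants in the pooled summary, the relevant dose is the first vimseltinib dose.
3. List records opened only for a lower grade, but do not count them as new TEAEs.

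Naming the last pre-dose grade as the reference matters. Without it, an event at Grade 2 before dosing that falls to Grade 1 and returns to Grade 2 afterwards could be counted as a rise, although it never exceeded its pre-dose grade. The placebo-period records must stay available for linking and grade comparison even though they are excluded from the pooled counts.

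The cost is SAP wording, a small programming step and slightly lower TEAE counts. Data collection does not change, and genuine new events and worsenings are still counted.
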